9.4.3 Electrocardiogram

A summary of raw values and changes from baseline will be provided by treatment group at each scheduled time point during the TE period for the following standard 12-lead ECG measurements: PR, QT, QTc for heart rate (HR) interval (QTcF), QRS duration, and HR.

The number and percentage of subjects with at least 1 PCS event during the TE period will be summarized overall and by treatment group. The PCS criteria for ECG data are provided in [Appendix E](#).

A listing containing individual subject ECG assessments will also be provided.

9.4.4 Vital Signs

The raw values and change from baseline values during the TE period will be summarized by treatment group at each scheduled time point: systolic and diastolic blood pressure (mm Hg), body temperature (°C), HR (beats per minute [bpm]), and respiratory rate (breaths per minute).

The number and percentage of subjects with at least 1 PCS event during the TE period will be summarized overall and by treatment group. The PCS criteria for vital signs data are provided in [Appendix E](#).

A listing containing individual subject vital signs assessments will also be provided.

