Examination of surgical site			X ^h	X	X	X		X	X
Vital signs ^g	X							X	X
Standard 12-lead ECG ⁱ	X		X ^j						
Serum chemistry and hematology	X		X ^k	X	X			X	X
Coagulation studies	X		X ^k						
Urinalysis	X		X ^k						
Serum samples for immunogenicity tests ^m	X		X ⁿ	X	X	X			

^g Vital signs and full physical examinations will be performed at Screening, Early Termination, and Safety Follow-up Visits as applicable; symptom-directed vital signs and symptom-directed physical examinations will be performed at other study visits. Vital signs will be assessed following a 5-minute rest in the supine position.

^h The Post-Surgery examination of surgical site will be performed within the time period following the completion of surgery and 7 days after surgery.

ⁱ The subject will be instructed to rest in the supine position for at least 5 minutes before having an ECG performed. The ECG will be performed before any other procedures that may affect heart rate, such as blood draws. Additional ECGs are to be performed as appropriate (see Section 11.6.4).

^j The Post-Surgery ECGs will be obtained between 4 and 6 hours and between 12 and 14 hours after treatment.

^k The Post-Surgery clinical laboratory tests will be collected between 24 and 48 hours after treatment.

^l [REDACTED]

^m Serum samples for immunogenicity tests will also be collected at the time of any SAE occurring within 3 days after treatment.

ⁿ The Post-Surgery serum sample for immunogenicity tests will be collected 7 days after treatment or upon hospital discharge if discharge occurs earlier than 7 days after treatment.

Table 3-1 Study VX15-210-101 Schedule of Assessments

Event/Assessment	Screening ^a	Surgery ^b	Post-Surgery ^c	6-Week Follow-up (± 7 Days) ^d	3-Month Follow-up (± 7 Days) ^d	6-Month Follow-up (± 7 Days) ^d	12-Month Follow-up (± 7 Days) ^d	Early Termination ^d	Safety Follow-up 28 (± 3) Days After Treatment ^{d,e}
Adverse events and prior and concomitant medications and procedures	Continuous from signing of ICF through the last study visit								
Efficacy Assessments									
ISNCSCI examination ^o	X			X	X	X	X	X	X
SCIM III ^o				X	X	X	X	X	X
GRASSP Quantitative Prehension ^o						X		X	X
CUE-T ^o						X		X	X
Hospitalizations	Continuous from signing of ICF through the last study visit								
Study Drug Administration									
VX-210 or placebo		X							
Pharmacokinetic Assessments									
Serum samples for PK	X ^q	X ^q	X ^q						

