8.1.4 Early Discontinuation

Early Termination Visit will be conducted when a subject withdraws or is withdrawn from the study (Section 9.4), or 1 or multiple study sites are closed (Section 13.2.7). Assessments at the Early Termination Visit are listed in Table 3-1. The Safety Follow-up Visit will be required in addition to the Early Termination Visit only for subjects who prematurely terminate from the study prior to Day 28 after treatment. Subjects who prematurely terminate from the study subsequent to Day 28 after treatment will only be required to complete the Early Termination Visit.

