11.6.3 Vital Signs and Surgical Site and Physical Examinations

The surgical site will be examined for proper wound healing and lack of infection at time points indicated in [Table 3-1](#).

A physical examination of all body systems and vital signs assessments will be performed at the Screening, Early Termination, and Safety Follow-up Visits (see [Table 3-1](#)). At other visits, symptom-directed physical examinations and symptom-directed vital sign assessments can be performed at the discretion of the investigator or healthcare provider.

A physical examination should include a review of the following systems: head/neck/thyroid; eyes/ears/nose/throat (EENT); respiratory; cardiovascular; abdomen; skin; musculoskeletal; and neurological. Breast, anorectal, and genital examinations will be performed when medically indicated. After screening, any clinically significant abnormal findings in physical examinations will be reported as AEs.

Vital signs include blood pressure (systolic and diastolic), temperature, pulse rate, and respiration rate. These will be assessed following a 5-minute rest in the supine position. After screening, any clinically significant findings in vital signs will be reported as AEs.

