9.4 Safety Analysis

All safety summaries will be based on the set of data associated with the TE period for subjects in the Safety Set.

The overall safety profile of VX-210 will be assessed in terms of the following safety and tolerability endpoints:

- Incidence of treatment-emergent adverse events (TEAEs)
- Clinical laboratory values (i.e., hematology, serum chemistry, coagulation studies, and urinalysis)
- ECGs
- Vital signs

All safety data will be presented in individual subject data listings.

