Vital signs ^g	X							X	X
Standard 12-lead ECG ⁱ	X		X ^j						
Serum chemistry and hematology	X		X ^k	X	X			X	X
Coagulation studies	X		X ^k						
Urinalysis	X		X ^k						
Serum samples for immunogenicity tests ^m	X		X ⁿ	X	X	X			

^g Vital signs and full physical examinations will be performed at Screening, Early Termination, and Safety Follow-up Visits as applicable; symptom-directed vital signs and symptom-directed physical examinations will be performed at other study visits. Vital signs will be assessed following a 5-minute rest in the supine position.

^h The Post-Surgery examination of surgical site will be performed within the time period following the completion of surgery and 7 days after surgery.

ⁱ The subject will be instructed to rest in the supine position for at least 5 minutes before having an ECG performed. The ECG will be performed before any other procedures that may affect heart rate, such as blood draws. Additional ECGs are to be performed as appropriate (see Section 11.6.4 of the protocol).

^j The Post-Surgery ECGs will be obtained between 4 and 6 hours and between 12 and 14 hours after treatment.

^k The Post-Surgery clinical laboratory tests will be collected between 24 and 48 hours after treatment.

Serum samples for immunogenicity tests will also be collected at the time of any SAE occurring within 3 days after treatment.

ⁿ The Post-Surgery serum sample for immunogenicity tests will be collected 7 days after treatment or upon hospital discharge if discharge occurs earlier than 7 days after treatment.

Event/Assessment	Screening ^a	Surgery ^b	Post-Surgery ^c	6-Week Follow-up (± 7 Days) ^d	3-Month Follow-up (± 7 Days) ^d	6-Month Follow-up (± 7 Days) ^d	12-Month Follow-up (± 7 Days) ^d	Early Termination ^d	Safety Follow-up 28 (± 3) Days After Treatment ^{d,e}
Adverse events and prior and concomitant medications and procedures	Continuous from signing of ICF through the last study visit								
Efficacy Assessments									
ISNCSCI examination ^o	X			X	X	X	X	X	X
SCIM III ^o				X	X	X	X	X	X
GRASSP Quantitative Prehension ^o						X		X	X
CUE-T ^o						X		X	X
Hospitalizations	Continuous from signing of ICF through the last study visit								
Study Drug Administration									
VX-210 or placebo		X							
Pharmacokinetic Assessments									
Serum samples for PK	X ^q	X ^q	X ^q						

^o Conducted by an independent, trained assessor (e.g., physiatrist/occupational therapist/physical therapist).

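### Vital signs are a named safety endpoint with planned change-from-baseline and PCS tables, but a subject who completes the study has no scheduled post-dose reading to put in them

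*SAP*

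**What the plan says.** SAP 9.4 and protocol 12.3.4 name four safety endpoints: TEAEs, laboratory values, ECGs and vital signs. The SAP introduces them this way: "The overall safety profile of VX-210 will be assessed in terms of the following safety and tolerability endpoints".

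For vital signs, SAP 9.4.4 and protocol 12.3.4.4 plan two summaries, and the SAP adds an individual listing:

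- By time point: "The raw values and change from baseline values during the TE period will be summarized by treatment group at each scheduled time point". This covers blood pressure, temperature, heart rate and respiratory rate.
- PCS: "The number and percentage of subjects with at least 1 PCS event during the TE period will be summarized overall and by treatment group".

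Collection is set out in protocol 11.6.3: "A physical examination of all body systems and vital signs assessments will be performed at the Screening, Early Termination, and Safety Follow-up Visits". The schedule in SAP Appendix A agrees: "Vital signs and full physical examinations will be performed at Screening, Early Termination, and Safety Follow-up Visits as applicable". For other visits, protocol 11.6.3 says that "symptom-directed vital sign assessments can be performed at the discretion of the investigator or healthcare provider", while the footnote to protocol Table 3-1 is firmer: "symptom-directed vital signs and symptom-directed physical examinations will be performed at other study visits".

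Protocol 8.1.4 limits who has the two post-dose visits. Early Termination follows withdrawal or closure of a site. On the other visit it says: "The Safety Follow-up Visit will be required in addition to the Early Termination Visit only for subjects who prematurely terminate", and only if they leave before Day 28.

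**The concern.** The analysis sections plan tables that the collection schedule cannot fill for most subjects. Someone who attends every visit has a screening value and nothing scheduled after dosing. The table by scheduled time point would hold only early leavers, whether they withdrew or their site closed. For completers, a PCS value could come only from a reading taken because of symptoms.

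At stake is how the safety report is read. A low PCS percentage could look reassuring when few subjects were measured, and a high one could look like a signal when measurement followed symptoms. A difference between arms could reflect who left or who was measured rather than the drug.

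**Working it through.** There is no stated figure to reproduce. The check sets the schedule against the planned output.

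**1. Scheduled post-dose data for a completer** (protocol Table 3-1, SAP Table 12-1, SAP 9.4.2 to 9.4.5)

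| Data | Scheduled post-dose readings | Planned output |
|---|---|---|
| ECG | 4–6 h and 12–14 h | change from baseline, PCS, listing |
| Chemistry, hematology | 24–48 h, 6 weeks, 3 months | change from baseline, PCS, listing |
| Coagulation | 24–48 h | change from baseline, PCS, listing |
| Full physical examination | none | listing only |
| Vital signs | none | change from baseline, PCS, listing |

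The same output suits ECGs and laboratory tests because their readings exist. Physical examinations share the vital-sign schedule and the same footnote, and they are only listed. Vital signs alone have summary tables and no scheduled post-dose reading in completers. The row and footnote are legible in both documents and agree with protocol 11.6.3, so redaction or table extraction does not explain the gap.

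**2. What reaches the PCS table.** SAP 9.1 admits unscheduled readings to maximum and minimum derivations, so symptom-directed values can enter PCS counts. Every criterion in SAP Table 12-6 combines an absolute threshold with a change from baseline, so a subject with no post-dose reading cannot be classified. The table covers heart rate and systolic and diastolic pressure only. Temperature and respiratory rate therefore depend wholly on the by-time-point table. SAP 9.4.4 states no denominator for the PCS percentage.

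**3. Which Early Termination readings count.** Take a subject who leaves after Day 28 and so has no Safety Follow-up Visit.

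- Protocol 12.3.1: the treatment-emergent period ends at 28 days, so the Early Termination reading is outside it.
- SAP 9.1: the period runs to the later of 28 days and the last available visit, so the same reading is inside it.

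**4. Number contributing (illustration only).** The documents give about 50 subjects per arm and 10% withdrawal before the first follow-up (protocol 12.1, SAP 7.2).

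- 0.10 × 50 = 5 per arm with a scheduled reading and 50 − 5 = 45 without, if every such subject attends a termination visit and nobody leaves later.
- Assumed range of 5% to 20% for total early termination: 0.05 × 50 = 2.5 to 0.20 × 50 = 10 per arm.
- Effect of the unstated denominator: one PCS subject is 1/5 = 20% of those measured but 1/50 = 2% of the arm.
- Exact two-sided 95% upper limit after zero events, 1 − 0.025^(1/n): 52.2% for n = 5 and 7.1% for n = 50. This shows only how little a zero from five subjects rules out. It does not predict the planned table.

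**The case against.** The strongest reply is that little turns on these tables. They are descriptive, and no test or stated stopping rule uses them. Continuous summaries report n, so a sparse table would show that it is sparse. The individual listing is already planned, and the IDMC safety reviews have their own analysis plan, which is not among these documents. All of this stands, and it limits the consequence. It does not rescue the PCS percentage, whose denominator is unstated and whose numerator depends on who was measured.

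Four stronger readings are tempting, and the documents do not support them.

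- A reader might infer that the acute post-dose period goes unobserved. Two post-surgery ECGs are scheduled, SAP 9.4.3 summarises their heart rate, and the ECG heart-rate PCS thresholds in Table 12-5 match those in Table 12-6. Protocol 11.6.3 also has clinically significant vital-sign findings reported as AEs. The gap is routine blood pressure, temperature and respiratory rate.
- A reader might infer that all the vital-sign data come from dropouts. That fits scheduled readings only, and even those include subjects whose site closed. Symptom-directed readings may come from anyone.
- A reader might take 5 per arm as the expected number. The 10% counts withdrawal before the first follow-up, not total early termination. Protocol 9.4 bars evaluations after consent is withdrawn and only asks sites to request a termination visit, which lowers the number. Later withdrawals and site closures raise it.
- A reader might count the missing vital-sign window in SAP Appendix B as further evidence. ECG and coagulation have no window there either, and Safety Follow-up uses the nominal visit, so this adds little.

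**Conclusion.** The point holds as a mismatch between schedule and analysis. As written, neither vital-sign table supports an interpretable between-arm comparison of blood pressure, temperature or respiratory rate. A completer has no scheduled post-dose reading; this follows from the text and needs no assumption. How many subjects would have one cannot be fixed from the documents, and the figures in step 4 rest on assumed attendance and withdrawal.

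No direction of bias is shown. The PCS percentage could come out too low or too high, depending on the denominator and on who was measured. The primary efficacy analysis is untouched. The point should be corrected because it concerns a named safety endpoint and the correction is cheap, but it does not threaten the trial's main conclusion.

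**What to change.** **Main change.** Reconcile Table 3-1 with protocol 12.3.4.4 and SAP 9.4.4 in one of two ways.

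1. Replace the by-time-point and PCS percentage tables with the listing already planned, as for physical examinations, and adjust the endpoint lists in protocol 12.3.4 and SAP 9.4 to match.
2. If PCS counts are kept, use the number of subjects with a post-dose reading as denominator, show scheduled and symptom-directed readings separately, and state that vital signs do not support a between-arm safety conclusion.

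**Alongside it.** Adopt one definition of the treatment-emergent period in protocol 12.3.1 and SAP 9.1, so that it is clear whether Early Termination readings after Day 28 count. Align the footnote to Table 3-1 with protocol 11.6.3 on whether symptom-directed readings at other visits are required or discretionary.

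**Optional addition.** Where inpatient vital signs around the existing post-surgery ECG times are already charted, transcribe them to the CRF and summarise those. That such charting exists is an assumption.

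**Cost.** The main change is wording plus minor programming, and SAP section 4 allows revisions before the final database lock and unblinding. The optional addition needs a CRF change late in the study and retrospective data entry for subjects already dosed, across approximately 45 sites. Charted readings would not be standardised as a study measurement would be.

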9.4.5 Physical Examination

Physical examination, including surgical site examination, results will be presented in individual subject data listings only.

After screening, any clinically significant abnormal findings in physical examinations will be reported as AEs.

9.4.6 Other Safety Analysis

Not applicable

10 SUMMARY OF INTERIM AND IDMC ANALYSES

10.1 Interim Analysis

An interim analysis will be conducted when approximately 33% of enrolled subjects have completed the 6-month follow-up visit. Based on the results of this interim analysis, the study may continue or stop for futility. The IDMC will conduct review of this interim analysis and make recommendation to the sponsor. If the study is considered unsuccessful at the time of the interim analysis, the study is to be terminated, study enrollment is to be stopped, and subjects are to be followed for safety reasons only.

Based on the review of the data provided at the interim analysis meeting, the IDMC will make a recommendation regarding whether the study should continue or should stop for futility. The guideline for futility stopping will be that the 9-mg dose group improves in UEMS by less than approximately 1.19 points over placebo for the approximately 33% of subjects analyzed, under the assumed standard deviation (SD) of 6.

The IDMC will review the observed SD at the time of the interim analysis. If the SD deviates from the assumption, the futility guide is adjusted to be that the study will be stopped for futility if conditional power (under observed primary endpoint treatment effect size) is <10.6% or the observed primary endpoint treatment effect size is <1.19. The following table presents examples of the futility boundary with respect to different sizes of SD. The last column refers to the minimum observed primary endpoint effect size that is required to achieve statistical significance under the given size of SD at the final analysis.

Table 10-1 Guidelines for Futility Stopping

Standard Deviation	Futility Boundary	Conditional Power (Under	Minimum Required Observed
---------------------------	--------------------------	---------------------------------	----------------------------------

		Observed Effect Size)	Effect Size at Final Analysis
4	1.19	25.1%	1.7
6	1.19	10.6%	2.5
8	1.59	10.6%	3.3
10	1.98	10.6%	4.1

In all analyses supporting this interim analysis, only the first 43 randomized subjects will be used unless otherwise specified; this sub-population includes approximately 33% of enrolled subjects who are dosed with placebo or 9-mg of VX-210 and who will have completed the 6-month follow-up visit at the time of the interim analysis data cut.

10.1.1 Interim Background Characteristics

- **Subject disposition:**

The number of subjects in the following categories will be summarized overall and by treatment group based on the All Subjects Set:

- Randomized or dosed (All Subjects Set)
- Randomized
- Dosed (Safety Set)
- Full Analysis Set

The number and percentage (based on the Full Analysis Set) of subjects in each of the following disposition categories will be summarized overall and by treatment group:

- 6-Month Follow-up Visit Occurred
- Completed study
- Prematurely discontinued the study and the reasons for discontinuation

A listing will be provided for disposition, including the subjects who discontinued study with reasons for discontinuation.

- **Demographics and baseline characteristics:**

Demographics and baseline characteristics will be summarized overall and by treatment group based on the Full Analysis Set.

Demographic data will include the following:

- Sex (female and male)
- Age (in years)
- Age group (<30 versus \geq 30 years of age)

- Ethnicity (Hispanic or Latino, not Hispanic or Latino, and not collected per local regulations)
- Race (White, Black or African American, Asian, American Indian or Alaska Native, Native Hawaiian or Other Pacific Islander, not collected per local regulations, and Other)
- Country

Baseline characteristics will include the following:

- Weight (kg)
- Height (cm)
- BMI (kg/m²)
- AIS Grade (A or B with or B without sacral pinprick preservation)
- Baseline UEMS score (total, left and right)

- **Prior and concomitant medications:**

Medications used will be coded as described in section 9.2.3.

A given medication may be classified as follows: prior, concomitant, post-treatment, both prior and concomitant, both concomitant and post-treatment, or prior, concomitant, and post-treatment.

If a medication has a completely missing or partially missing start/stop date and it cannot be determined whether it was taken before the dose date, concomitantly, or after the TE period, it will be classified as prior, concomitant, and post-treatment. No imputation rules for missing or partial medication start/stop dates are applied.

Prior medications and concomitant medications will be summarized descriptively using frequency tables by (1) by preferred names; (2) anatomic class (ATC) level 1, ATC level 2, and preferred names.

Summaries of medications will be based on the Full Analysis Set.

Post-treatment medications will be listed by subject.

10.1.2 Interim Efficacy Analysis

For the interim futility analysis data review meeting, the IDMC will be provided with statistical analyses of the following primary and secondary study endpoints and supportive data listings as appropriate. For all the interim efficacy analyses, no *P* value will be provided. All the efficacy endpoints aforementioned will be analyzed based on the FAS.

- Change from baseline in the UEMS score at 6 months after treatment: The UEMS score will be summarized at baseline, 6 weeks, 3 months, 6 months, and 12 months after treatment using the descriptive summary statistics by treatment group. The change from baseline in the UEMS score at 6 weeks, 3 months, 6 months, and 12 months after treatment will also be summarized descriptively by treatment group. The MMRM analysis of the change from baseline in the UEMS score at 6 months after

treatment in the interim analysis is similar to the MMRM analysis of the same variable in the primary analysis (see section 9.3.1.2) except for that no *P* value will be provided.

- **SCIM III Self-Care subscore at 6 months after treatment:** The SCIM III Self-Care subscore at 6 weeks, 3 months, 6 months, and 12 months after treatment will be summarized descriptively by treatment group. The analysis of the SCIM III self-care subscore at 6 months after treatment will be based on an ANCOVA model, which will include the SCIM III self-care subscore at 6 months after treatment as the dependent variable, and treatment as a fixed effect, with adjustment for age and AIS grade (only including A versus B with sacral pinprick preservation versus B without sacral pinprick preservation) at baseline. If the SCIM III self-care subscore at 6 months after treatment is missing after the visit windows rules have been applied, the score at the early termination visit will be carried forward for the analysis. The estimated mean treatment effect (LS means difference) at 6 months after treatment and a 95% CI will be provided. No *P* value will be provided.
- **CUE-T score at 6 months after treatment:** The CUE-T score at 6 months after treatment will be summarized descriptively by treatment group. The ANCOVA analysis of the CUE-T score at 6 months after treatment is similar to the ANCOVA analysis of the SCIM III Self-Care subscore at 6 months after treatment in the interim analysis except for that the relevant endpoint here is the CUE-T score at 6 months after treatment.
- **GRASSP Quantitative Prehension score at 6 months after treatment:** The GRASSP Quantitative Prehension score at 6 months after treatment will be summarized descriptively by treatment group. The ANCOVA analysis of the GRASSP Quantitative Prehension score at 6 months after treatment is similar to the ANCOVA analysis of the SCIM III self-care subscore at 6 months after treatment in the interim analysis except for that the relevant endpoint here is the GRASSP Quantitative Prehension score at 6 months after treatment.
- **AIS grade conversion from baseline at 6 months after treatment:** The definition of an AIS responder is same as that in the primary analysis (see section 9.3.2.1). The AIS grade at baseline, 6 weeks, 3 months, 6 months, and 12 months after treatment will be summarized descriptively by treatment group. The AIS responder at 6 weeks, 3 months, 6 months, and 12 months after treatment will also be summarized descriptively by treatment group.
- **Motor level change from baseline at 6 months after treatment:** The definition of a motor level is same as that in the primary analysis (see section 9.3.2.1). The motor level at baseline, 6 weeks, 3 months, 6 months, and 12 months after treatment will be summarized descriptively by treatment group. The motor level responder at 6 weeks, 3 months, 6 months, and 12 months after treatment will also be summarized descriptively by treatment group.

